# 10.4 Suspected Unexpected Serious Adverse Reactions (SUSARs)

An Adverse Event or Suspected Adverse Reaction is considered a SUSAR if it is serious, unexpected, and suspected. Prior to reporting to the applicable Regulatory Authorities, the IND Sponsor will evaluate the available evidence and to judge the likelihood that the drug actually caused the adverse event. The SUSAR must be reported to FDA within 15 days, or if fatal or life threatening, within 7 days, by the IND Sponsor. The IND Sponsor must report an adverse event as a suspected adverse reaction only if there is evidence to suggest a causal relationship between the drug and the adverse event. Additionally, potential Hy's law cases will be reported as SUSARs.

The applicable Regulatory Authorities shall be notified by Sponsor Safety Physician of any SUSAR, as per local Regulatory Authorities guidelines and timeframe specified as per local regulation.

May 20, 2022 Protocol: **AS012-20-01** Page 57 of 88

All participating Investigators, IEC/IRB and other stakeholders shall be notified of any SUSAR by CRO's Medical Monitor as per local regulatory requirement.

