6. STATISTICAL METHODS OF ANALYSIS

6.1 General Principles

The statistical analyses will be performed by Quartesian LLC, with approval of the Sponsor, using SAS Version 9.4 (or higher). All tables, figures and listings will be produced in landscape format.

In general, all data will be listed by subject and visit/time point where appropriate. The summary tables will be stratified by, or have columns corresponding to, treatment groups.

The total number of subjects in the treatment group (N) under the specified population will be displayed in the header of summary tables.

Data will be summarized using descriptive statistics for continuous variables. Unless otherwise specified, descriptive statistics will include number of subjects, mean, standard deviation, minimum, median and maximum. Number of subjects with missing values will also be displayed, but only if non-zero. The minimum and maximum statistics will be presented to the same number of decimal places as the original data. The mean and median will be presented to one more decimal place than the original data. The standard deviation will be presented to two more decimal places than the original data.

In summary tables of categorical variables, counts and percentages will be displayed. The count [n] indicates the actual number of subjects in a particular category, which should always be less

than or equal to the total number of subjects in the respective study group with known (non-missing) category [M]. Percentage will be obtained by: % = n/M*100. Unless otherwise specified, all percentages will be expressed to one decimal place.

All statistical tests will be two-sided at a significance level of $\alpha = 0.05$, unless otherwise indicated.

Baseline will be defined as the last assessment, scheduled or not, prior to the first dose of the study drug, unless otherwise specified.

In by-visit summaries, only data collected on scheduled visits/timepoints will be summarized. Data from unscheduled assessments will be included in listings and may be used in determination of baseline if applicable.

Relative days will be calculated relative to date of first dose of the study drug. Relative days will be calculated as follows only when the full assessment date is known (i.e., partial dates will have missing relative days).

For assessment on or after the day of first dose of the study drug:

Relative Day = Date of Assessment – Date of First Dose of Study Drug+1.

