6.11.2 Laboratory tests

A central laboratory will be used for all assessments unless noted otherwise. The laboratory assessments include:

Thyroid function: at study Visits 1, 7, and 12 (screening and Weeks 24 and 52) a blood sample will be collected for free T4 and TSH testing.

Hematology: at all study visits a blood sample will be collected for total and differential WBC count, Absolute Neutrophil count (ANC), Absolute Lymphocyte count (ALC), Platelet count, Hemoglobin, Hematocrit.

Lipid profile: at the study Visits 1, 2, 7, and 12 (Screening and study Weeks 1, 24, and 52) a blood sample will be collected for LDL, HDL and total cholesterol and triglycerides testing. The test does not need to be repeated at study Visit 2 if the screening assessment (visit 1) was performed within 2 weeks of Visit 2.

Clinical chemistry: at all study visits a blood sample will be collected for sodium, potassium, chloride, calcium, magnesium, bicarbonate, phosphate, blood urea nitrogen, random glucose, albumin, total protein, alkaline phosphatase, creatinine, Alanine aminotransferase (ALT), AST, gamma glutamyl transferase (GGT), total bilirubin, conjugated bilirubin testing.

Coagulation profile: at the study Visits 1, 2, 7, and 12 (Screening and study Weeks 24, and 52) a blood sample will be collected for PT and INR testing. The test does not need to be repeated at study Visit 2 if the screening assessment (Visit 1) was performed within 2 weeks of Visit 2.

Serology: at Screening visit a blood sample will be collected for: HIV antibodies, HBsAg, and HCV antibodies testing.

Serum pregnancy test: at Screening visit a blood sample will be collected for serum beta-hCG testing.

The following tests will be performed at a clinic site:

Urinalysis dipstick: at the study Visits 1 to 12 (Screening and study Weeks 1 to 52) a urine sample will be collected for pH, specific gravity, protein, glucose, ketones, and blood testing. The test does not need to be repeated at study Visit 2 if the screening assessment (Visit 1) was performed within 2 weeks of Visit 2.

Microscopic exam may be performed at the local or central laboratory at the discretion of the investigator if the dipstick is positive (i.e., trace or above). Only dipstick results will be available in the study database.

Urine Pregnancy Test: at all study visits a urine sample will be collected in women of childbearing potential and the results of all pregnancy tests (positive or negative) will be documented.

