A positive result should be confirmed by a different brand of UPT. A confirmed positive urine pregnancy test during the treatment periods of the study requires immediate interruption of study treatment and the subject must be discontinued from the study.

For hematology, chemistry, thyroid function, and coagulation profile the labs that were abnormal and clinically significant at end of treatment (Week 52) are needed at safety follow-up visit (Week 64).

Hematology, chemistry (including lipid profile and thyroid function, and coagulation parameters and their changes from baseline will be summarized descriptively by visit and treatment group. Urinalysis dipstick results will be summarized categorically (positive or negative).

Shifts from baseline among the categories Normal (within the reference range), Low (below the reference range), and High (above the reference range) will be presented by visit.

All results will be listed.

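### The SAP plans no table that counts, by treatment, subjects with graded or joint aminotransferase and bilirubin elevations, although the protocol singles out potential Hy's law cases

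*SAP*

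**What the plan says.** **Collection.** SAP 6.11.2, in line with protocol 5.5, states: "Clinical chemistry: at all study visits a blood sample will be collected for" a panel that includes "alkaline phosphatase, creatinine, Alanine aminotransferase (ALT), AST, gamma glutamyl transferase (GGT), total bilirubin, conjugated bilirubin testing". Protocol 5.5 also lets the investigator order unscheduled laboratory tests in response to adverse events.

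**Analysis.** SAP 6.11.2 plans three outputs for blood tests:

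- Descriptive summaries of values and changes, by visit and treatment group. Under SAP 6.1, "descriptive statistics will include number of subjects, mean, standard deviation, minimum, median and maximum".
- A categorical analysis, made separately at each visit: "Shifts from baseline among the categories Normal (within the reference range), Low (below the reference range), and High (above the reference range) will be presented".
- A listing of all results.

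The section has one other categorical summary, which is not of a blood test: "Urinalysis dipstick results will be summarized categorically (positive or negative"). SAP 6.1 limits by-visit summaries to scheduled visits; unscheduled values are listed and may serve to define baseline.

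**Special status of liver cases.** Protocol 10.4 states: "Additionally, potential Hy's law cases will be reported as SUSARs". The visible text gives no biochemical criterion for such a case. The visible SAP does not mention Hy's law, multiples of the upper limit of normal, a worst post-baseline value, or a combination of two tests.

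**The concern.** The protocol gives expedited status to one event that is defined by laboratory values, yet the SAP has no summary built to count it. I assume, because the documents do not define it, that a potential Hy's law case involves an aminotransferase rise together with a bilirubin rise in the same subject. A three-level shift for a single test at a single visit can express neither the degree of a rise nor its coincidence with another test.

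At stake is the comparison across groups. The study has four AS012 groups and a placebo group, and treatment lasts 52 weeks. Whether liver elevations increase with dose is a question that a dose-ranging report should answer from prespecified counts. Under the present plan, someone would have to search listings by hand, perhaps after unblinding and with cut-offs chosen once the data are in view.

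**Working it through.** The plan states no figure on this point, so there is none to reproduce. The check asks what the planned outputs can and cannot determine. All subject counts and multiples below are assumed for illustration.

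**Inputs**
- Arm size n = 64 (approximate; SAP 3.2).
- Scheduled chemistry samples after Day 1 on treatment (protocol 7.3 to 7.12): Weeks 4, 12, 16, 20, 24, 28, 36, 44, 48 and 52. That is 5 up to Week 24 plus 5 after it, 10 in all.

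**Step 1: size within one test.** Any value above the reference range is High, so 1.1, 2.9, 3.1 and 10 times the upper limit share one category. With 6 of 64 subjects above the limit, the cell reads 6/64 = 9.4% in each of these cases:

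| Case | ALT in the 6 subjects | Shift table | Maximum |
|---|---|---|---|
| A | 6 at 1.1 times | 6 (9.4%) | 1.1 times |
| B | 1 at 10 times, 5 at 1.1 times | 6 (9.4%) | 10 times |
| C | 3 at 10 times, 3 at 1.1 times | 6 (9.4%) | 10 times |

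The maximum separates A from B and C. It does not separate B from C. The mean and SD would differ between B and C, but neither is a count of subjects above a threshold.

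**Step 2: two tests in one subject.** If a subjects are High on ALT and b are High on bilirubin at a visit, the number High on both lies between max(0, a + b − n) and min(a, b).

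- a = 3, b = 2: max(0, 3 + 2 − 64) = 0 and min(3, 2) = 2, so 0 to 2.
- a = 5, b = 3: max(0, 5 + 3 − 64) = 0 and min(5, 3) = 3, so 0 to 3.

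The single-test tables therefore do not fix the joint count. The separate maxima of ALT and bilirubin do not fix it either, since they may come from different subjects.

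**Step 3: across visits.** By-visit counts do not give the number of subjects ever affected. One subject High at each of the 10 visits could be the same subject throughout or 10 different subjects.

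**Step 4: unscheduled samples.** Protocol 5.5 allows them when an adverse event occurs. SAP 6.1 leaves them out of by-visit summaries. A peak caught only on such a sample enters neither the shift table nor the descriptive maximum; it appears only in the listing.

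**The case against.** The case for leaving the SAP as it is has real content.

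- **Nothing promised is missing.** Protocol 9.7 promises laboratory shifts and no inferential safety analysis. The SAP delivers the shifts and adds descriptive summaries and listings. Protocol 10.4 is an expedited-reporting rule, not an analysis commitment. A reader might infer that SAP and protocol contradict each other; they do not.
- **Size is not wholly hidden.** A reader might infer that a large elevation would leave no trace in the tables. By-visit maxima of values and of changes would show it for one test at a scheduled visit, including in a subject who was already High at baseline.
- **Cases can be traced.** A reader might infer that cases reported under 10.4 could not be reconciled with the data. Protocol 5.7 counts abnormal laboratory findings as adverse events. Serious treatment-emergent events are tabulated by treatment under SAP 6.11.1, and both events and laboratory results are listed by subject.
- **Detection is handled elsewhere.** Protocol 12.3 assigns targeted safety laboratory data to an independent monitor at the CRO. Protocol 10.1 reports no safety signal to date.
- **Some material is not visible.** Table shells are in a separate document (SAP 9), and parts of both documents are redacted.

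All of this stands, and it limits the point. It does not supply a count. Adverse event tables depend on an event being reported and coded, and SAP 6.11.1 shows no liver category. Listings need a search by hand. Monitoring during the trial is not a comparison across doses in the report.

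**Conclusion.** The point holds as a gap in the safety analysis and an inexpensive improvement. It is not an error or an inconsistency. For blood chemistry, no planned output visible in the SAP counts by treatment the subjects with graded aminotransferase elevations or with aminotransferase and bilirubin raised together. Unscheduled values are left out of every by-visit summary.

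The size is a matter of what cannot be determined: in the examples, the planned tables leave the joint count anywhere from 0 to 2, or from 0 to 3, in an arm of 64. The documents give no expected rate of liver events, so no probability of missing a signal is claimed.

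The conclusion rests on two assumptions: that the sponsor's Hy's law criterion combines the two kinds of test, and that neither the redacted text nor the separate shells already contain such a table.

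**What to change.** Add one paragraph to SAP 6.11.2 that specifies:

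1. A per-subject table of the worst post-baseline value, by actual treatment, using all post-baseline samples including unscheduled ones. It should show ALT or AST and total bilirubin in multiples of the upper limit of normal, and the number of subjects who meet the joint elevation.
2. A plot of peak ALT against peak bilirubin, one point per subject, marked by treatment.
3. The joint criterion, taken from whatever definition the sponsor already applies under protocol 10.4 and written into the SAP so that the table and the reported cases can be reconciled. No reporting threshold is proposed here.

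Because placebo subjects move to AS012 at Week 24, values should be assigned by treatment at the time of the sample, using the groups in SAP 6.1.1. Part I should also be shown separately. Placebo then has 5 scheduled post-baseline samples, as does each AS012 group, whereas over the whole treatment period it would be 5 against 10.

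The cost is one table and one figure from data already collected, with no added sampling or visits. If the shells already include these outputs, a sentence in 6.11.2 pointing to them is enough.

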6.11.3 Vital signs

Vital signs, including blood pressure, pulse rate, respiratory rate, and oral body temperature, will be documented at every visit. Vital signs will be measured after the subject has rested in a seated or supine position for at least 5 minutes.

Vital signs and their changes from baseline will be summarized descriptively by visit and treatment group.

All vital signs will be listed.

6.11.4 12-Lead ECG

Digital ECG devices will be used to record 12-lead ECGs at the Screening visit to confirm the subject's eligibility criteria as well as at study Weeks 12, 24, 36, 52, and 64. To avoid impacting results and quality of data, ECG should be done before other invasive or stressful procedures.

The following ECG parameters will be obtained directly from the computerized 12-lead ECG recordings: rhythm, ventricular rate, P-R interval, R-R interval, QRS duration and QT. QTcF will be calculated according to the Fridericia formula. Overall interpretation will be recorded as Normal, Abnormal not clinically significant or Abnormal clinically significant.

Heart rate and intervals as well as their changes from baseline will be summarized descriptively by visit and treatment group. Overall interpretation will be summarized by presenting number and percentage of subjects with each interpretation by visit and treatment group.

All ECG findings will be listed.

6.11.5 Physical Examination

The investigator, sub-investigator or appropriately delegated designee will perform a physical examination, prior to the Subject starting study drug and at the end of treatment. The physical examination will include, at a minimum, examination of the Subject's general appearance, comprehensive skin examination, HEENT (head, eyes, ears, nose and throat), heart, lungs, musculoskeletal system, neurological system, lymph nodes, abdomen and extremities. Each body system will be classified as normal, abnormal not clinically significant or abnormal clinically significant.

Number and percentage of subjects with normal, abnormal not clinically significant or abnormal clinically significant findings will be presented by body system, visit and treatment group.

All results will be listed.

6.11.6 Prior and Concomitant Medication

[figure not shown]
Prior and concomitant medication will be coded according to the World Health Organization – Drug Dictionary, Version SEP 01, 2020 and the Anatomical Therapeutic Chemical classification system. Prior medications are defined as those taken before the first dose of the study drug (i.e., start and end date before the first dose of the study drug). Concomitant medications are defined as those taken at the time of or after the first dose of the study drug. Any medications that were started before the first dose of the study drug but continued after dosing will be considered a concomitant medication.

All previous and concomitant medication will be listed by subject. Concomitant medications will be summarized by treatment group, Anatomic-Therapeutic-Chemical (ATC) class (highest level available) and preferred name. This analysis will be done for the Safety population.

For subjects re-randomized from Placebo in Part I of the study to an AS012 dose in Part II, any medication that was taken concomitantly with both study drugs will be counted under both.

A medication will be assigned to Part I if it was taken at least once between the date of the first study drug dose and the date of the Week 24 visit; for subjects who discontinue prior to Week 24 visit, all their concomitant medications will be assigned to Part I. Medication will be considered as taken after Part I if it was taken at least once after the date of the Week 24 visit.

The summary of concomitant medications will be presented in three ways:

All prior and concomitant medications will be listed.

7. INTERIM ANALYSIS

An IA to assess the primary efficacy endpoint will be conducted following the last patient Week 24 visit, once all subject VASI data have been cleaned and soft-locked. The IA for the primary efficacy assessment is planned for Week 24 in order to minimize the exposure of study subjects to placebo, and at the same time assess for efficacy at the earliest time point a

clinical response to treatment could be expected. Analysis outputs will be generated when the last subject has completed 24 weeks of study participation, and may include results for all planned endpoints up to Week 24. At the time of interim analysis at Week 24, the randomization will be unblinded to the sponsor and its designee. The final study database will be locked following last patient last visit at Week 64, once all subject data have been cleaned, and all coding of terms (AE, Concomitant Medications, Medical History) has been finalized.

Investigational sites, subjects, and study team members directly involved in study activities will remain blinded to study treatment assignments until the last subject completes their double-blind follow-up period (Week 64). A designated list of blinded and unblinded study personnel shall be maintained. Sharing of subject-level unblinded information for the IA will be confined to a designated unblinded study team. For the 24-week primary end-point, patient level data will not be provided to the site staff and the blinded study team. The Final CSR will be provided to the PI at the end of the study.

7.1 Content of the interim analysis

A subset of tables, listings and figures to be produced for the interim analysis will be identified in an appendix to this SAP.

7.2 Data cut-off for the interim analysis

The interim analysis will occur after the last subject's Week 24 visit. At this time subjects enrolled in the study earlier will progress well past Week 24 visit and their data from later visits will be present in the study database. While the primary focus of the interim analysis will be on the efficacy at Week 24, all available efficacy data entered into the database up to the pre-defined cut-off date will be used for analysis.

For analyses of safety, only the data up to Week 24 will be used. Any safety finding collected up to 24 visit as well as any adverse events or concomitant medications up to the date of the subject's Week 24 visit will be considered for the purposes of the interim analysis. Adverse events or concomitant medications that started prior to Week 24 visit and ended after it will be considered ongoing.

7.3 Unblinding for the interim analysis

A separate unblinding programming team will be allocated to perform the final run of the interim analysis. A separate "unblinded" folder will be created that will be accessible by the unblinded team only. Analysis programs will be prepared by the main study team, who will remain blinded at the time of the interim analysis and until the final database lock. Once all programs are ready and tested on blinded data, the programs will be transferred to the "unblinded" folder. After the data for the interim analysis are locked, randomization information will be released to the unblinded team only and saved in the "unblinded" folder. The unblinded team will run the analysis programs using the randomization information to produce unblinded tables, listing and figures.

9. LIST OF PLANNED TABLES, FIGURES, AND LISTINGS

[figure not shown]
See separate document with the table, figure and listing shells.

11. APPENDICES

[figure not shown]

[figure not shown]

Statistical Analysis Plan Study Code AS012-20-01 Version Amendment 1 Final Date Jul 27, 2022

Statistical Analysis Plan Study Code AS012-20-01 Version Amendment 1 Final Date Jul 27, 2022

11.2 Code Fragments

11.2.1 Primary analysis of the primary endpoint with multiple imputations

Step1. Efficacy data needs to be transposed to one record per subject structure with responses from Week 12 and Week 24 visits in different variables. In the examples below responses from Week12 and Week24 visits are denoted as CHG12 and CHG24.

Step 2. Impute intermittent missing values 50 times:

```
proc mi data=... out=... nimpute=50 seed=122001;
  var trtp disstab skinclass base chg12 chg24;
  class trtp disstab skinclass;
  fcs regpmm(chg12=trtp disstab skinclass base chg24);
  fcs regpmm(chg24=trtp disstab skinclass base chg12);
run;
```

Note: pre-specified seed is necessary to ensure results are repeatable and amenable to validation by double-programming. The value is chosen arbitrarily based on the protocol number.

Meaning of the variables:

- TRTP: treatment group
- DISSTAB: disease stability (stable/unstable)
- SKINCLASS: Skin type group (I-II, III-IV or V-VI)
- CHG12: response, i.e. VASI change from baseline, at Week 12
- CHG24: response, i.e. VASI change from baseline, at Week 24
- BASE: baseline value of VASI

Step 3. Analysis of imputed data. For each of the 50 imputations perform the primary analysis:

```
proc mixed data=... method=type3;
  by _imputation_;
  class trtp disstab skinclass;
  model chg24 = trtp disstab skinclass base;
  lsmeans trtp / diff=control('PLACEBO');
run;
```

Note: the input dataset is the output from the previous step. _Imputation_ variable is the imputation number from PROC MI output.

Step 4. Combine multiple imputation results:

```
proc mianalyze parms=...;
  by trtp;
  modeleffects trtp;
run;
```

Note: the input dataset (parms option) is LS Means or LS Means Differences (Diffs) dataset from the model from the previous step.

11.2.2 Sensitivity analysis of the primary endpoint with multiple imputations based on placebo scores

This analysis proceeds similar to the primary analysis in the previous section, except in Step 2 an additional statement is added to PROC MI to base the imputation on placebo scores only and consequently treatment group effect is removed from the imputations model:

```
proc mi data=... out=... nimpute=50 seed=122001;
  var disstab skinclass base chg12 chg24;
  class trtp disstab skinclass;
  fcs regpmm(chg12 chg24);
  mnar model (chg12 / modelobs = (trtp = 'PLACEBO'))
    model (chg24 / modelobs = (trtp = 'PLACEBO'));
run;
```

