#### 4. STUDY POPULATION

# 4.1 Number of Subjects

Approximately 320 subjects will be enrolled in the study in a 1:1:1:1:1

The number of subjects contributed by a site will not exceed approximately 10% of total study population unless approved by the Sponsor. Approximately 192 subjects will be enrolled in US sites and approximately 128 subjects will be enrolled in sites in India.

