#### 8.5 Randomization

At visit 2 the subject will be randomized to one of five treatment groups and the subject number will be assigned by an Interactive Response Technology (IRT). At visit 7 the active treatment will be reassigned for the Placebo group by IRT. Randomization and re-randomization will be stratified by stability of disease (stable vs. non-stable)

IRT using global data across all sites.

At visits 2, 4, 7, 9, and 11 the IP kit number corresponding to the subject's treatment group will be assigned by IRT using kit numbers available at a site.

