### 9.2 Sample Size Rationale

The study will randomize approximately 320 subjects into 5 treatment arms (n=approximately 64 subjects per arm) in a 1:1:1:1 ratio. The sample size assumes a drop-out rate of about 20%, with 52 evaluable subjects per treatment arm at the time of analysis. The study is powered at 85%, and assumes a two-sample Z-test with equal variances, two-sided alpha ( $\alpha$ ) of 0.05, a Baseline VASI mean of 15.7 and standard deviation of 8.9 (Hamzavi et al, 2004) and an improvement at Week 24 of 35% ( $\Delta$  5.50) for AS012 versus an improvement for placebo of 10% ( $\Delta$  1.56), for a mean treatment difference of 3.94. Since the correlation between Baseline and Week 24 VASI scores is expected to be >0.5, the standard deviation of the difference is conservatively estimated at 70% of the Baseline SD, or 6.4. Randomization will be stratified by stability of disease (stable vs. non-stable)

With a total of six possible stratification levels, 52 evaluable subjects per treatment arm ensures at least 8 subjects per stratification level.

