3.2 Sample Size

The study will randomize approximately 320 subjects into 5 treatment arms (n=approximately 64 subjects per arm) in a 1:1:1:1:1 ratio. The sample size assumes a drop-out rate of about 20%, with 52 evaluable subjects per treatment arm at the time of analysis. The study is powered at 85%, and assumes a two-sample Z-test with equal variances, two-sided alpha (α) of 0.05, a Baseline VASI mean of 15.7 and standard deviation of 8.9 and an improvement at Week 24 of 35% (Δ 5.50) for AS012 versus an improvement for placebo of 10% (Δ 1.56), for a mean treatment difference of 3.94. Since the correlation between Baseline and Week 24 VASI scores is expected to be >0.5, the standard deviation of the difference is conservatively estimated at 70% of the Baseline SD, or 6.4. The sample size takes into account an interim assessment of futility and efficacy, using an O'Brien-Fleming error spending function to determine the boundaries, once the placebo, dose reach 75% completion of the Week 24 VASI assessment. Randomization will be stratified by stability of disease (stable vs. non-stable) With a total of six possible stratification levels, 52 evaluable subjects per treatment arm ensures at least 8 subjects per stratification level.

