6.9.1.2 Primary analysis of the primary endpoint

The primary endpoint will be summarized descriptively by treatment group.

Note that approximately 5 sites will be designated to perform VASI, and VES by two independent assessors to test reliability and validity of the instruments (see Section 6.9.2.7). Only the assessment by the first assessor will be used for the primary endpoint.

The primary endpoint will be analyzed with an Analysis of Covariance (ANCOVA) model to compare change from baseline in VASI score results between treatment arms at Week 24. The ANCOVA model will include fixed effects for treatment, stability of disease (stable vs. non-stable at screening), and baseline VASI score as a covariate. Point estimates and 95% confidence intervals as well as p-values for the hypothesis of no difference will be obtained for the difference between each active dose versus placebo.

Type I error will be preserved in the primary efficacy analysis by use of a closed test step-down approach. Beginning with the highest total daily dose, pairwise comparisons to placebo will be made in the following sequence:

Number and percentage of subjects achieving these endpoints will be presented by treatment group along with 95% confidence interval for percentages based on binomial proportion.

Maintenance of these endpoint will be assessed by presenting the number and percentage of subjects maintaining these endpoints at Week 64 among those who achieved them at Week 52.

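### Country is in neither the strata nor the primary and imputation models; because the allocation ratio changes during enrolment, a country term should be added before the Week 24 unblinding

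*SAP*

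**What the plan says.** **Enrolment.** Protocol section 4.1: "Approximately 192 subjects will be enrolled in US sites and approximately 128 subjects will be enrolled in sites in India".

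**Strata.** Protocol section 8.5 names disease stability as a stratification factor; the text after it is cut. The surviving end of a sentence there reads "IRT using global data across all sites". Protocol section 9.2 adds: "With a total of six possible stratification levels, 52 evaluable subjects per treatment arm ensures at least 8 subjects per stratification level". The SAP code defines three skin type groups, so two stability levels by three skin groups account for all six levels.

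**Primary model.** SAP section 6.9.1.2: "The ANCOVA model will include fixed effects for treatment, stability of disease (stable vs. non-stable at screening), and baseline VASI score as a covariate". The code in SAP section 11.2.1 gives the fuller form, with skin type group: "model chg24 = trtp disstab skinclass base". The absence of skin type from the visible text may be a redaction and is not treated here as a discrepancy. The PROC MI calls in 11.2.1 and 11.2.2 use stability, skin type group, baseline and the Week 12 and Week 24 changes (with treatment in 11.2.1). Neither contains country.

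**Allocation.** Part I starts at 3:3:1:3:1 (placebo first) and later moves to 1:1:3:1:3. The synopsis and protocol section 8.4 put the switch at about 55% of enrolment. Protocol section 3 and SAP section 3.1 put it at about 45%. Protocol section 8.4 also prints the second ratio as 1:1:3:1:1. These statements need reconciling.

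**The concern.** Country is recorded for every subject before randomization and divides the trial 60/40. VASI is scored by local investigators. The protocol's own prohibitions (excessive sun, phototherapy, herbal vitiligo preparations) show that it regards such exposures as able to affect the outcome. It is a reasonable inference, though not a documented fact, that mean change could differ between the two countries beyond what three skin type groups explain.

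Two things follow if it does. First, the country difference sits in the residual variance and lowers power slightly. Second, and more important, each arm draws a different fraction of its subjects from each allocation stage. If the country mix differs between stages, so does the country mix between placebo and the arms whose ratio moves the opposite way. That gap is systematic, and the planned standard error does not describe it.

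**Working it through.** **Inputs from the documents:** 192 US and 128 India of 320; treatment difference 3.94; SD of change 6.4; 64 randomized and 52 evaluable per arm; 85% power. SAP section 3.2 "assumes a two-sample Z-test with equal variances, two-sided alpha (α) of 0.05". **Assumed:** D, the US-India difference in mean Week 24 change, and the timing of recruitment by country. Neither is given.

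**1. The plan's sample size.** Fixed design: n = 2 × (1.960 + 1.036)² × 6.4² / 3.94² = 47.4, so 48 per arm. At 52 per arm, SE = 6.4 × √(2/52) = 1.255 and power is Φ(3.94/1.255 − 1.960) = 88.1%. With the O'Brien-Fleming interim look at 75% that SAP section 3.2 describes (bounds 2.340 and 2.012), plus an assumed beta-spending futility rule of the same type, power at 52 is 85.1%, which reproduces the stated 85%. The comparisons below use the fixed-design figure.

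**2. Precision under a constant ratio.** Shares are 192/320 = 0.60 and 128/320 = 0.40. The fraction of variance due to country is R² = 0.4 × 0.6 × D² / 6.4², and the adjusted SD is 6.4 × √(1 − R²).

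| D | R² | Adjusted SD | Power at 52 | n for 85% |
|---|---|---|---|---|
| 0 | 0% | 6.400 | 88.1% | 48 |
| 1 | 0.6% | 6.381 | 88.3% | 48 |
| 2 | 2.3% | 6.325 | 88.8% | 47 |
| 3.94 | 9.1% | 6.102 | 90.9% | 44 |

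The gain is 0 to 2.8 points. These are upper bounds, because the formula treats country as unrelated to skin type group.

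**3. Chance imbalance.** The SD of the difference in India share between two arms of 64 is √(2 × 0.4 × 0.6/64) = 8.7 points. A gap above 10 points occurs in about 25% of arm pairs. This is ordinary sampling variation.

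**4. Systematic imbalance, 55/45 split.** Stage 1 has 176 subjects and stage 2 has 144.
- Placebo: 176 × 3/11 + 144 × 1/9 = 48 + 16 = 64, so 75% come from stage 1.
- Each opposite-ratio arm (third and fifth positions): 176 × 1/11 + 144 × 3/9 = 16 + 48 = 64, so 25% come from stage 1.
- If India is 20% of stage 1 (35.2 subjects), it is (128 − 35.2)/144 = 64.4% of stage 2.
- India share in placebo: 0.75 × 0.20 + 0.25 × 0.644 = 31.1%.
- India share in an opposite-ratio arm: 0.25 × 0.20 + 0.75 × 0.644 = 53.3%.
- Gap: 22.2 points. Shift for D = 2: 0.222 × 2 = 0.44 VASI points.

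| India in stage 1 / stage 2 (55/45 split) | Gap | Shift at D = 2 |
|---|---|---|
| 40% / 40% | 0 | 0 |
| 30% / 52% | 11 points | 0.22 |
| 20% / 64% | 22 points | 0.44 |
| 0% / 89% | 44 points | 0.89 |

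Under the 45/55 split, with India at 30%, 20% and 0% of stage 1, the gaps are 9, 18 and 35 points. The two arms that share placebo's ratio have no systematic gap.

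**5. What a shift of 0.44 does.** 0.44/1.255 = 0.35 SE. Two-sided type I error for that contrast becomes Φ(−1.61) + Φ(−2.31) = 6.4% instead of 5%. If the shift goes against the drug, fixed-design power falls to Φ(3.139 − 0.35 − 1.960), about 80%. This step assumes dropout unrelated to country.

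**The case against.** The strongest reply is that the analysis is already sound. The coded model contains both stratification factors and baseline VASI. Leaving out another covariate that was not stratified on does not in itself bias the estimate or raise the type I error, and chance imbalance in country is already covered by the standard error and confidence interval. All of that stands. A reader might infer that country is a known prognostic factor, or that the primary ANCOVA is invalid without it. The documents support neither: the visible text gives enrolment counts by country but no country effect, and the protocol prohibits the exposures most likely to differ.

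It is also fair that D = 3.94 would be a country difference as large as the whole target effect, and that rater differences arise between investigators and sites, which one US/India term cannot separate.

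The redactions limit what can be said about secondary or sensitivity analyses. Parts of SAP section 6.9 are cut and section 6.10 is not visible, so a country analysis may exist there. That does not affect the primary model or the two imputation models, whose code is printed in full.

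What the reply does not answer is the change of ratio. The no-bias argument needs each arm to draw the same country mix in expectation. That fails if the ratio and the country mix change together.

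**Conclusion.** The omission is real and worth correcting, but it is not an error in the ANCOVA. With a constant ratio or the same country mix in both stages, it costs at most about 2.8 power points over the assumed range of D. The conditional risk is larger: for two of the four active arms, differing recruitment times would produce a systematic country gap, with a shift of roughly 0.2 to 0.4 VASI points for D = 2 and a gap of 11 to 22 points, against a target of 3.94. Both D and the recruitment timing are assumptions, so the bias is possible and not demonstrated. The visible documents do not show which dose sits in which ratio position, so it cannot be said whether the first comparison in the step-down sequence is one of those affected. A country term removes the country part of any such shift. It would not remove a time trend unrelated to country.

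**What to change.** Before the Week 24 unblinding described in SAP section 7:

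- Add country (US, India) as a fixed effect in the primary ANCOVA, in the text of SAP section 6.9.1.2 and in the PROC MIXED code of 11.2.1.
- Do the same in the ANCOVAs for the key secondary endpoints (VES and VIPs change at Week 24).
- Add country as a predictor in both PROC MI models (11.2.1 and 11.2.2), so that the imputation and analysis models agree.

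The cost is one degree of freedom, one already available variable in the code and a sentence of SAP text. If country does prove unbalanced between arms, the adjusted standard error widens slightly, which is the price of removing the shift. Adding the term after unblinding would be post hoc.
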